3.4. Per-Protocol Analysis Set

The per-protocol (PP) analysis set will consist of all patients who have completed the study without any violations of the inclusion/exclusion criteria or any violations or omissions of the drug administration.

The efficacy analysis for the primary and secondary endpoints will be repeated for the per-protocol analysis set.

4. GENERAL ISSUES FOR DATA ANALYSIS

4.1. General

Descriptive statistics for continuous variables include count (n), mean, SD, standard error (SE), median, minimum, and maximum. In addition, for fremanezumab concentration, percentage coefficient of variation (%CV) and geometric mean will also be calculated. Descriptive statistics for categorical variables include patient counts and percentages, and a missing category will be displayed as appropriate.

Summaries of potentially clinically significant abnormal values for clinical laboratory tests and vital signs values will include all postbaseline values (including scheduled, unscheduled, and early withdrawal visits).

4.2. Specification of Baseline Values

Baseline is the last observed data before the administration of the first dose of the IMP, unless otherwise noted. For data collected in the e-diary daily, baseline will be derived from the run-in period (including days from the informed consent up to the day prior to the first dose of the IMP administration) and prorated to 28 days if the number of days in the run-in period is not equal to 28. Details are provided in Section 6.1.

4.3. Region of Pooled Countries

The study is planned to be conducted in approximately 12 countries. The countries will be pooled to 2 regions (US/Canada and other).

4.4. Handling Withdrawals and Missing Data

For efficacy analyses using e-diary data, the missing data handling methods are provided in Section 6.1.4. For the efficacy analyses using non-e-diary data, missing data handling methods, if applicable, will be provided in the efficacy analysis section for that endpoint.

Dates that have incomplete information, such as only the month and year or just the year, will be estimated for the purpose of calculating variables that are dependent on time if necessary. Day will be estimated as the first day (01) of the month (if month and year of partial date are available) or middle (July 1) of the year (if only year is available), month will be estimated as July if year and day are available, unless otherwise noted. The imputations for partial dates are only for calculation purpose. Original date variables will not be imputed. Listings will list dates as collected.

Patients' date of birth will be collected by IRT. IRT will record the date of birth as the first day of the first month (January first) when only year is captured, and the first day of the selected month when month and year are captured.

4.5. Study Days and Visits

For by-visit summaries, if there are multiple assessments at a postbaseline visit then the last non-missing assessment at that visit will be used for the summary (this includes scheduled and

unscheduled assessments), except for triplicate ECG assessments (see Section 8.11 for further details).

Study visits are detailed in Table 1.

Table 1: Study Visits

Visit #	V1	V2	V3	V4	V5
Week #	Week -1	Week 0	Week 4	Week 8	Week 12
Visit	Screening	Baseline	Visit 3	Visit 4	EOT/early withdrawal (84 ±3 days)

Notes: EOT=end of treatment; V2/Week 0 is day 1, which is the day eligible patients are randomized and receive first dose of IMP.

‘Last Assessment’ may be derived for analysis purpose and is defined as the last observed postbaseline data. For patients who withdraw from the study early, their data at the early withdrawal visit will be excluded from the by-visit sections but will be included in the Last Assessment section.

Study days are numbered relative to the first day of the IMP administration. The start of treatment (day 1) is defined as the date on which a patient takes the first dose of the IMP, as recorded on the case report form (CRF). Days will be numbered relative to treatment start (ie, ..., -2, -1, 1, 2, ...; with day 1 being the first day of the IMP administration and day -1 being the day before the first day of the IMP administration).

For data from the e-diary, weekly analysis windows (week 1, week 2, etc.) and 4-week/monthly analysis windows (weeks 1 to 4, weeks 5 to 8, and weeks 9 to 12) will be derived for the purpose of efficacy endpoint analyses. Details are provided in Section 6.1.3.

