### **9.3.1. Handling Withdrawals and Missing Data**

Efficacy variables from patients who do not have diary data completed for the entire study period will be imputed. For the analyses based on the proportion of responders, patients who are terminated from the study early will be considered as nonresponders. For patients who complete the study and have intermittent missing days in the e-diary, data will be prorated to 7 days. Details will be provided in the statistical analysis plan.

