Use of oxygen will be recorded in the e-diary. The 12-week period is the period from administration of the first dose of the IMP to the EOT/early withdrawal visit. The weekly average number of days using oxygen for a patient during the 12-week period will be calculated and prorated to 7 days using formula [1B]. Missing data handling method is provided in Section 6.1.4.2.

Data will be analyzed using an ANCOVA method in a manner analogous to the primary endpoint as described in Section 6.2.2.

6.3.5. Patient-Perceived Satisfactory Improvement at 1, 4, 8, and 12 Weeks After Administration of the First Dose of the IMP Relative to Baseline

The PPSI scale will be completed in the e-diary at home at week 1(day 7) and in the investigational site tablet at the visits 2, 3, 4, and 5. Patients will mark the level of CH-associated pain and indicate the level of pain using the following scale compared with 4 weeks ago:

- 1 = Much worse
- 2 = Moderately worse
- 3 = Slightly worse
- 4 = Unchanged
- 5 = Slightly improved
- 6 = Moderately improved

- 7 = Much improved

PPSI will be defined as change in pain that corresponds with a minimal rating of “slightly improved” (Protocol Section 6.7). For analysis purpose, a dichotomous scale of “Responder” (scales 5 to 7) or “Non-responder” (scales 1 to 4) will be derived.

The percentage of patients in dichotomous scale of “Responder” or “Non-responder” at week 1, visit 3, 4, and 5 will be analyzed using a CMH method in a manner analogous to the first secondary endpoint as described in Section 6.3.1.

Modification to SAS code in Section 6.3.1: adding a ‘by’ statement for visit.

Raw scales will be summarized using descriptive statistics. A missing category will be presented if applicable.

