7. MULTIPLE COMPARISONS AND MULTIPLICITY

Hochberg's step-up method will be implemented to test primary and secondary endpoints while controlling the overall type 1 error rate at 0.05.

The treatment comparisons will be for the fremanezumab 900-mg iv loading dose group versus placebo [H_{01}] and the fremanezumab 675-mg sc loading dose group versus placebo [H_{02}]. According to Hochberg step-up method, the rules of multiple comparisons for 2 null hypotheses for the primary endpoint are as follows:

1. If the resulting 2-sided p-values from both comparisons are ≤ 0.05 (reject both null hypotheses), then the next comparison of interest will be interpreted inferentially at the alpha level of 0.05 and statistical significance will be claimed for both active dose groups. Testing of secondary efficacy measures will be continued.
2. If the resulting 2-sided p-value from 1 of comparisons is > 0.05 (fail to reject the null hypothesis) and other resulting 2-sided p-value is ≤ 0.025 ($\frac{\alpha}{2} = 0.025$; reject the null hypothesis), then the result from the comparison with p-value ≤ 0.025 will be interpreted inferentially at the alpha level of 0.05, and statistical significance will be claimed for this active dose group. No further comparisons will be interpreted inferentially.
3. If the resulting 2-sided p-value from both comparisons are > 0.05 (fail to reject both null hypotheses), then no statistical significant will be claimed and no comparisons will be interpreted inferentially.

If the resulting 2-sided p-values from both comparisons for the primary endpoint are ≤ 0.05 (reject both hypotheses; case 1 as described above), testing of secondary efficacy measures will proceed at an error rate of 0.05 in the sequential manner as specified in Section 1.2. The same testing rules as described above will be followed. This process will continue either until all comparisons of interest for secondary endpoints are interpreted inferentially or until the point at which the resulting 2-sided p-value for a comparison of interest is > 0.05 . At the point where a 2-sided p-value > 0.05 , the testing process stops. No further comparisons will be interpreted inferentially.

For the last secondary endpoint (PPSI assessments), only the assessment at week 12 will be included in the multiple comparisons.

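### The week-12 PPSI test has no rule for early withdrawals, so it compares only patients who have a visit-5 rating

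*SAP*

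**What the plan says.** - **Collection.** Protocol Appendix B lists the PPSI among the procedures of the combined end-of-treatment/early withdrawal visit. Under SAP 6.3.5 the week-1 rating is entered in the e-diary and the others "in the investigational site tablet at the visits 2, 3, 4, and 5".
- **Analysis.** SAP 6.3.5 splits the seven-point scale into Responder (5 to 7) and Non-responder (1 to 4). The percentage "at week 1, visit 3, 4, and 5 will be analyzed using a CMH method in a manner analogous to the first secondary endpoint". The code from SAP 6.3.1 is changed only by "adding a ‘by’ statement for visit".
- **Withdrawals.** SAP 4.5: "For patients who withdraw from the study early, their data at the early withdrawal visit will be excluded from the by-visit sections". It keeps those data for a Last Assessment section, which SAP 6.3.5 does not use.
- **Missing values.** SAP 4.4: "For the efficacy analyses using non-e-diary data, missing data handling methods, if applicable, will be provided in the efficacy analysis section for that endpoint". SAP 6.3.5 mentions missing values only as a display category for the raw scale.
- **Multiplicity.** For PPSI, SAP 7 says that "only the assessment at week 12 will be included in the multiple comparisons".
- **Protocol.** For analyses of the proportion of responders, Protocol 9.3.1 says that "patients who are terminated from the study early will be considered as nonresponders". Protocol 9.5.4.3 defines that proportion by a reduction of at least 50% in monthly attacks.

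**The concern.** A patient enters the FAS with one dose and 10 days of postbaseline diary data (SAP 3.3). Someone who leaves at week 6 is normally in the FAS but has no visit-5 rating, and nothing tells the programmer how to classify that patient. The derived outcome has only two categories, both defined by a recorded score, so the patient falls in neither. A test in the type I error-controlled sequence then rests on a group defined after randomisation. Protocol 3.4 and 4.3 name lack of efficacy and adverse events as reasons for withdrawal, so being absent at week 12 may well be related to response. The per-protocol repeat does not help, because SAP 3.4 limits that set to patients who completed the study.

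**Working it through.** **1. What happens to one patient.** Take a FAS patient who withdraws at week 6.
- SAP 4.5 keeps the withdrawal-visit rating out of by-visit sections. The PPSI test is run by visit, so on a plain reading it is covered.
- SAP 4.4 sends the reader to the endpoint's own section for a missing-data rule. SAP 6.3.5 has none for the test.
- SAP 6.3.5 models the test on SAP 6.3.1, which points to SAP 6.1.4.2. That section prorates counts over recorded diary days. A single tablet rating has no days to prorate.
- By contrast, SAP 6.4.7 scores a missing percent reduction as 0, that is, as no response.

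The patient therefore adds to neither numerator nor denominator at week 12.

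**2. The plan's own figures (SAP 2.4).** Difference 4, SD 8, two-sided alpha 0.05, power 90%, discontinuation 14%.
- n per arm = 2 × (1.960 + 1.282)² × (8/4)² = 84.1, so 85.
- At 86 per arm: 4 / (8 × √(2/86)) = 3.28; 3.28 − 1.96 = 1.32; power 0.906.
- 258 / (1 − 0.14) = 300.

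The stated sample size reproduces.

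**3. Patients lost from the PPSI test.** 300 × 0.14 = 42, or 14 per arm, leaving about 86 of 100 per arm. This is an upper figure for the FAS, which already excludes patients with fewer than 10 diary days.

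**4. Equal 14% dropout.** The response rates are assumptions; the documents give none. The nonresponder-scored rate is the observed rate × 0.86. Power = Φ[(d − 1.96 s₀)/s₁], where d is the difference, s₀ its pooled standard error and s₁ its unpooled standard error.

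| Observed rates | Difference | Power, n = 86 | Nonresponder-scored rates | Difference | Power, n = 100 |
|---|---|---|---|---|---|
| 30% v 50% | 20 points | 0.77 | 25.8% v 43.0% | 17.2 points | 0.73 |
| 40% v 60% | 20 points | 0.75 | 34.4% v 51.6% | 17.2 points | 0.69 |
| 50% v 70% | 20 points | 0.77 | 43.0% v 60.2% | 17.2 points | 0.69 |

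**5. Unequal dropout averaging 14% over the three arms.** Assume the nonresponder-scored rate p is the same in both arms, between 30% and 50%. The observed rate is then p / (1 − dropout). Each row is one comparison at two-sided 0.05, where 2.5% is expected in each direction.

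| Dropout, placebo / each active arm | Observed difference, active − placebo | Chance of a significant result in that direction |
|---|---|---|
| 6% / 18% | +4.7 to +7.8 points | 9.6% to 17.8% |
| 10% / 16% | +2.4 to +4.0 points | 5.2% to 7.6% |
| 18% / 12% | −2.5 to −4.2 points | 5.3% to 7.9% |
| 22% / 10% | −5.1 to −8.5 points | 10.3% to 20.1% |

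First row at p = 30%: 0.30/0.94 = 31.9%, 0.30/0.82 = 36.6%, difference 4.7 points. Steps 4 and 5 start from 100 randomised patients per arm, so within the FAS the effects would be somewhat smaller.

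**The case against.** **The exclusion in SAP 4.5 is defensible.** The sentence can be read as a rule for table layout. PPSI asks about change from 4 weeks ago, so a rating given at withdrawal is not a week-12 rating. This stands. The fault is not that the withdrawal rating is kept out of week 12, but that SAP 6.3.5 does not say how a patient without a week-12 rating enters the test. Table 1 of the SAP does share one column between end of treatment and early withdrawal, but the sentence below it rules out treating them alike.

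**A reader might infer that the SAP breaks a protocol requirement.** Protocol 9.3.1 is worded for analyses of the proportion of responders, SAP 6.3.5 uses the labels Responder and Non-responder, and SAP 17 declares no changes. But Protocol 9.5.4.3 ties the term to attack reduction, Protocol 6.7 does not call PPSI a responder endpoint, and the SAP Introduction gives the SAP precedence. Applying 9.3.1 to PPSI is arguable, not settled. On the narrow reading, no rule exists. On the broad reading, the SAP does not carry over a rule that does.

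**A reader might also infer that withdrawal-visit scores for EQ-5D, HADS, SF-12 and WPAI should be moved to the next scheduled visit.** The documents do not support this. Those analyses are exploratory, their repeated-measures models keep visit-3 data from patients who leave later, and moving a score would misstate when it was given.

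**Conclusion.** The gap is real. As written, the week-12 PPSI test compares only patients with a visit-5 rating and leaves out up to about 42 of 300 at the planned discontinuation. Nonresponder scoring is the better-defined choice, and it matches how SAP 6.4.7 treats missing values.

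The size is modest if dropout is equal: under the assumed rates, about 3 points of difference and 0.04 to 0.08 of power. It would go too far to infer that the test is seriously biased. Measured against nonresponder scoring, substantial bias needs withdrawal that differs by arm. It can then favour or disfavour active treatment, and the documents give no arm-specific withdrawal rates.

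The consequence is also limited. PPSI is the last of six secondary endpoints and is reached only if both comparisons are significant on the primary and on the five secondaries before it.

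**What to change.** In SAP 6.3.5, state that a FAS patient with no week-12 PPSI rating because of early withdrawal is counted as a Non-responder in the Cochran-Mantel-Haenszel test. Keep the observed-case analysis as a sensitivity analysis. The same sentence may be used for the Patient Global Impression of Change in SAP 6.4.9.6. Reconcile Protocol 9.3.1 with 9.5.4.3 so that it is clear whether the nonresponder rule covers PPSI.

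The cost is a short SAP amendment before unblinding and a small change to the derivation code. Reported response rates will be slightly lower, and power slightly less if dropout is equal across arms.

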5. STUDY POPULATION

5.1. General

The ITT analysis set (see Section 3.1) will be used for all study population summaries unless otherwise specified. Summaries will be presented by treatment group and for all patients.

5.2. Patient Disposition

Data from patients screened; patients screened but not randomized and reason for not randomized; patients who are randomized; patients randomized but not treated; patients in the ITT, safety, and other analysis sets; patients who complete the study; patients who withdraw from the study; and patients continuing into the long-term safety study will be summarized using descriptive statistics. Data from patients who withdraw from the study will also be summarized by reason for withdrawal using descriptive statistics.

Patients who consent to the wearable sensor substudy and their completion status (completed and reason for not-completed the substudy) will be summarized using descriptive statistics.

This summary will include all patients.

5.3. Demographics and Baseline Characteristics

The demographic data will be collected at the screening visit after the patient signs the informed consent form. Patient's demographics data including age, age group (<40 years or ≥40 years), gender, race, race group (white or other), ethnicity, region (US/Canada or other), baseline weight (kg), baseline height (cm), and baseline body mass index (kg/m²) will be summarized using descriptive statistics for all analysis sets. For continuous variables, treatment groups will be compared using an analysis of variance (ANOVA) with treatment group as a factor. For categorical variables, treatment groups will be compared using a Pearson's chi-square (or Fisher's exact test if cell sizes are too small).

Baseline characteristics including years since first CCH diagnosis, preventive medication use (yes or no) at screening or baseline, use of any triptans/ergots during the run-in period (yes or no), and number of CH attacks during the run-in period will be summarized for the ITT analysis set using descriptive statistics. No inferential analyses will be performed.

The years since first CCH diagnosis will be calculated as (date of informed consent - first date of CCH diagnosis + 1)/365.25. Rules for handling partial CCH diagnosis date are in Section 4.4.

5.4. Medical History

All medical history abnormalities will be coded using the Medical Dictionary for Regulatory Activities (MedDRA). The incidence of medical history abnormalities will be summarized using descriptive statistics by system organ class (SOC) and preferred term. Patients are counted only once in each SOC and only once in each preferred term.

5.5. Prior Therapy and Medication

All prior medications or therapy will be coded using the World Health Organization Drug Dictionary of medical codes (WHO Drug). The incidence of prior medications or therapy will be

summarized by therapeutic class and preferred term using descriptive statistics. Patients are counted only once in each therapeutic class category, and only once in each preferred term category. Prior medications will include all medications taken prior to the administration of the first dose of the IMP.

The prior medications will be summarized by the following indications categories:

- preventive medication from Appendix H of the study protocol for CH
- preventive medication from Appendix H of the study protocol for other reason than CH
- butalbital for CH
- butalbital for other reason than CH
- triptans for CH
- triptans for other reason than CH
- ergots for CH
- ergots for other reason than CH
- non-steroidal anti-inflammatory drugs (NSAIDs) for CH
- NSAIDs for other reason than CH
- opioids for CH
- opioids for other reason than CH
- other

5.6. Childbearing Potential and Methods of Contraception

Information related to reproductive system findings will be collected at the screening visit. Data will be listed.

5.7. Physical Examinations

Patients with at least 1 abnormal finding (overall) and abnormal findings for each category will be summarized.

5.8. Study Protocol Deviations

Data from patients with any important protocol deviations during the study will be summarized overall and for each category using descriptive statistics.

6. EFFICACY ANALYSIS

6.1. General

The FAS will be used for all efficacy analyses unless otherwise noted. Analyses of the primary and secondary endpoints will be repeated for the PP analysis set.

For data not collected daily, baseline is the last observed data before the administration of the first dose of the IMP. For data collected daily in the e-diary, baseline will be derived from the run-in period (including days from the informed consent up to the day prior to the first dose of the IMP administration). Details are provided in Section 6.1.3. The efficacy baseline value derived from the run-in period are

- number of CH attacks
- number of CH attacks of at least severe severity
- number of days with use of cluster-specific acute headache medication (triptans and ergot compounds)
- number of days with use of any acute headache medication
- number of days oxygen is used
- severity of CH attacks

Summaries will be presented by treatment group as randomized unless otherwise noted. In addition to inferential statistics, descriptive statistics will be presented in by-visit or by-analysis-window summaries.

6.1.1. Cluster Headache Attacks Data from E-diary

CH attacks will be recorded in the e-diary daily. Corresponding CH attack questions are in [Appendix A](#) (questions A1, A2, and B1 through B15). Patients will record headache(s) occurred during last 48 hours. The recording window on e-diary device is “Yesterday morning 6:00 am to today at 5:59 am” or “The day before yesterday morning 6:00 am to yesterday at 5:59 am”; a maximum of 48 hours of recall time will be accepted to record CH attacks for the day before yesterday.

The derivation logics for CH attacks are in [Appendix B](#). A CH attack will be endorsed if required criteria in [Appendix B](#) are met.

Baseline and postbaseline average number of CH attacks for a patient within an analysis window will be calculated based on data available and prorated to 28 days using formula [1A] as the monthly average for analyses based on monthly windows or prorated to 7 days using formula [1B] as the weekly average or weekly value for analyses based on weekly average or weekly windows.

6.1.2. Data Derivation

The **monthly average** of an efficacy variable will be calculated and prorated to 28 days as follows:

$$\frac{\sum \text{efficacy endpoint data during the period}}{\text{Number of Days with assessments recorded in the eDiary during the period}} \times 28 \quad [1A]$$

The **weekly average or weekly value** of an efficacy variable will be calculated and prorated to 7 days as follows:

$$\frac{\sum \text{efficacy endpoint data during the period}}{\text{Number of Days with assessments recorded in the eDiary during the period}} \times 7 \quad [1B]$$

The “efficacy endpoint data” will be “number of CH attacks”, “days with use of cluster-specific acute headache medications (triptans and ergot compounds)”, “days oxygen is used to treat CCH”, or “days with use of any headache medication”, etc.

The period will be the run-in period (including days from informed consent up to the day prior to the first dose of the IMP administration) for baseline calculation or an analysis window (eg. weeks 1 to 4, weeks 5 to 8, weeks 9 to 12, etc.) for post-baseline calculations.

The **percentage of reduction** from baseline in the monthly average number of CH attacks will be calculated as follows:

$$\frac{\text{baseline value} - \text{postbaseline value}}{\text{baseline value}} \times 100\% \quad [2]$$

where baseline value and postbaseline value are the monthly average calculated using [1A].

Note, the calculation of a proportion based on the weekly average or monthly average would yield the same results. Therefore to be consistent, all proportions will be calculated based on the monthly average number of CH attacks.

